7.7.2 Clinical laboratory evaluations

Observed and change from OLE baseline clinical laboratory test data will be summarized descriptively for each scheduled visit and presented based on the safety set.

Shift from baseline to post-baseline laboratory findings at each visit in normal range criteria (Low, Normal, High) will also be summarized for chemistry and hematology tests.

The incidence of potentially clinically significant abnormalities (PCSA) for liver function (Table 4) for each scheduled visit will be summarized.

Parameter	PCSA Criteria		
Chemistry	Alanine transaminase (ALT) or Aspartate transferase (AST) >=3x Upper limit of normal (ULN)		
	ALT or AST >=5xULN		
	ALT or AST >=8xULN		
	ALT or AST >=3xULN and <5xULN, with Baseline >=2xULN		
	ALT or AST >=5xULN and <8xULN, with Baseline >=2xULN		
	ALT or AST >=5xULN with Baseline >=2xULN		
	Alkaline Phosphatase >=1.5xULN		
	Total Bilirubin >=2xULN		
	ALT >=3xULN and Total Bilirubin >=2xULN		
	Any Chemistry Test		
Hematology	White blood cells (WBC) <2.0 and >20,000 10 ³ cells/uL		
	Hgb:		

Table 4: Potentially	Clinically	Significant	Abnormality	(PCSA)	Liver	Abnormality
Criteria						

Version: Final 1.0 Date: 04MAY2023 Page 38 of 47

Statistical Analysis Plan (SAP) 🕌 🗙 E N O N

Parameter	PCSA Criteria
	Age 30-60 days: Hgb < 7 g/dL
	Age 61 days to 6 years: Hgb <9 g/dL
	Platelets (PLT) <50 x 10^3 cells/uL
	Any Hematology Test

A listing will be provided for clinical laboratory test data. The listing will include normal ranges and clinical laboratory values that are outside the normal ranges and potentially clinically significant abnormalities will be flagged in the listing.

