7.7.5 Electrocardiograms

Observed and changes from OLE baseline of continuous ECG measurements will be summarized by treatment group and age groups (1 to 12 months and >12 to 84 months) at each scheduled visit. Additional summaries will be provided for ECG interpretation and will be summarized using frequency tables. Shift from baseline to post-baseline will also be provided for the ECG interpretation.

Potentially clinically significant abnormality categories listed below will be summarized using count and percentage.

Variable Name	Age group	Criterion
	NA	<= 300
QT interval corrected for heart rate by		>= 60 msec increase from
Fridericia's formula (QTcF) (msec)		baseline
		>= 500
OT Interval (msec)	NA	<= 300
QT Interval (msec)		>= 600
	1 to 12 months	>= 86 or $>=25%$ increase
OBS Interval (maga)		from baseline
QRS Interval (msec)	>12 to 84	>= 95 or $>= 25%$ increase
	months	from baseline
DP Internal (maga)	1 to 12 months	>= 141 or >= 25%
PR Interval (msec)		increase from baseline
	>12 to 84	>= 155 or $>= 25%$ increase
	months	from baseline
Haart rate (hpm)	1 to 12 months	>= 194
Heart rate (bpm)		<= 106
Haart rate (hpm)	>12 to 84	>= 123
Heart rate (bpm)	months	<= 62

Table 6: Potentially Clinically Significant ECG Abnormality Criteria

Listings will be provided for ECG data and potentially clinically significant abnormalities will be flagged in the listing.

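### Most PCSA criteria can be met by an unchanged pre-existing abnormality, and the visible SAP text plans no count of new cases

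*SAP*

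**What the plan says.** Laboratory (SAP 7.7.2): "The incidence of potentially clinically significant abnormalities (PCSA) for liver function" is to be summarized at every scheduled visit. Some rows are plain limits, such as "Alkaline Phosphatase >=1.5xULN", "ALT >=3xULN and Total Bilirubin >=2xULN" and "Platelets (PLT) <50 x 10^3 cells/uL". Three ALT/AST rows also require a raised baseline, for example "ALT or AST >=3xULN and <5xULN, with Baseline >=2xULN". A shift table from baseline is planned, using the Low, Normal and High categories of the reference range.

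Vital signs (SAP 7.7.3): each of the four blood-pressure rows needs both a value outside the normal limits and a change of a given size. The two pulse rows use the limit alone.

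ECG (SAP 7.7.5): "Potentially clinically significant abnormality categories listed below will be summarized using count and percentage". QTcF has two absolute rows and one change row. QRS and PR are met by the limit or by a 25% increase. QT and heart rate have limits only. The ECG shift table covers the interpretation, not the intervals.

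General conventions (SAP 7.1): percentages use all subjects in the treatment group within the population of interest unless otherwise noted. Baseline for summaries is the last value before extension dosing. For the XEN496 Only group, that value is taken while already on drug. The derived-variables table in SAP 6.1 separately defines a double blind baseline, before study drug in XPF-009-301.

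**The concern.** Long-term safety is the primary objective (SAP section 2). Every child in the extension receives XEN496 and there is no randomized comparison (SAP 3.2), so the child's own pre-drug status is the main within-study means of telling a drug effect from the disease or from background antiseizure medication. If a child met a limit before the first XEN496 dose and stays there, the planned table counts that child at every visit alongside children whose abnormality is new. The ALT/AST rows conditioned on a raised baseline show that the sponsor allows for children entering with raised values. A reader of the PCSA tables could then take a stable background abnormality for a finding on XEN496, or fail to see a few new cases among many old ones.

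**Working it through.** **1. Which rows can an unchanged value meet?** Counted from the tables in SAP 7.7.2, 7.7.3 and 7.7.5. The two catch-all rows (any chemistry, any hematology test) are left out, and the WBC row is counted once with its two limits read as alternatives.

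| Block | Rows | Require a change | Can be met unchanged |
|---|---|---|---|
| Chemistry | 9 | 0 | 9 |
| Hematology | 4 | 0 | 4 |
| Vital signs | 6 | 4 (blood pressure) | 2 (pulse) |
| ECG | 13 | 1 (QTcF increase) | 12 |
| Total | 32 | 5 | 27 |

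Two groups mention baseline but still belong in the last column:
- QRS and PR (4 rows): limit or increase, so the limit alone is enough.
- The three ALT/AST rows with baseline at least 2xULN: no rise is required. A child at 4xULN before and after meets "ALT or AST >=3xULN and <5xULN, with Baseline >=2xULN".

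The other 20 rows (32 - 5 - 4 - 3) do not refer to baseline at all.

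**2. Can pre-existing cases be removed by subtraction?** For ALT/AST, in part. Write BL for baseline:
- (>=3x) - [(3 to <5x, BL>=2x) + (>=5x, BL>=2x)] = >=3x with BL<2x
- (>=5x) - (>=5x, BL>=2x) = >=5x with BL<2x
- (>=8x) - [(>=5x, BL>=2x) - (5 to <8x, BL>=2x)] = >=8x with BL<2x

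These identities held in all of 2,000 simulated sets of 40 children with one transaminase value per child per visit. There are two limits to them. The cut is at 2xULN and not at the PCSA limit, so a rise from 2.5x to 4x falls in the same row as a stable 4x. With two analytes the subtraction can also fail: take ALT going from 2.5x to 4x and AST from 1x to 6x, with baseline read per analyte. ALT puts the child in the 3 to <5x baseline row, and the first identity then removes the new AST case.

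No such split exists for alkaline phosphatase, bilirubin, ALT with bilirubin, hematology, pulse, QT, the absolute QTcF rows, heart rate, or the limit arm of QRS and PR.

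**3. Do the shift tables fill the gap?** No. Baselines of 1.1xULN and 5xULN are both High, so the table does not say whether a PCSA value was already PCSA at baseline. The visible text plans no shift table for vital signs.

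**4. Illustration of size.** The plan states no PCSA rate to reproduce. N = 40 is the approximate maximum in SAP section 4; all else is assumed: p0 = share already beyond the limit at baseline, s = share of those who stay beyond it, q = 5% true new rate among the rest.

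Counted = N x p0 x s + N x (1 - p0) x q

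| p0 | Counted, s = 1 | Reported | Share pre-existing | Reported, s = 0.5 |
|---|---|---|---|---|
| 0% | 0 + 2.0 = 2.0 | 5.0% | 0% | 5.0% |
| 5% | 2 + 1.9 = 3.9 | 9.8% | 51% | 7.3% |
| 10% | 4 + 1.8 = 5.8 | 14.5% | 69% | 9.5% |
| 20% | 8 + 1.6 = 9.6 | 24.0% | 83% | 14.0% |

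Restricting both count and denominator to children below the limit at baseline returns 5% each time: 1.9/38, 1.8/36, 1.6/32.

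**The case against.** The plan does not ignore baseline, and a reader who infers that every PCSA row counts any value beyond a limit would be wrong: five rows demand a change. The term incidence is used only for the laboratory table; vital signs get summaries and ECG gets counts and percentages. The liver rows, where that term appears, are the best handled, because transaminases can be split at 2xULN. The plan also has observed and change-from-baseline summaries, and listings that flag PCSA values. With about 40 children, a reviewer can trace each case. All of this stands, but none of it yields a tabulated count net of baseline at the PCSA limit.

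A second objection is that a treatment-emergent rule may exist elsewhere. The opening of 7.7 and the adverse event subsection are not in the supplied text, the Safety Set definition is redacted, and protocol 8.3.2 is listed in the contents only. The table shells are a separate document, and a summary for each scheduled visit may already show a baseline column. It would therefore be wrong to conclude that the plan has no such rule; what can be said is that none appears in the three PCSA sections or in 7.1.

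Third, baseline prevalence may be low. The extension excludes children with certain clinically significant conditions at screening/baseline and carries over the primary study's exclusions (protocol synopsis). That is fair: at p0 = 0 there is no distortion, and nothing in the documents shows that the higher values of p0 apply.

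Fourth, a careless remedy could do harm. Counting only what is new since the extension baseline would drop abnormalities that arose on XEN496 in the primary study. ECG limits also change at 12 months: if age is taken at the visit, an unchanged heart rate of 130 lies within the limits of the younger band (106 to 194) but meets the limit of 123 in the older one. Both objections stand and shape the fix.

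**Conclusion.** The point holds for 27 of 32 criteria rows, on the visible text. For those rows the planned counts mix abnormalities present before XEN496 with new ones, and in a study without a concurrent control the counts alone cannot show which arose on drug. How much they mix is unknown. The 9.8% to 24.0% range rests on an assumed 5% new rate, 5% to 20% baseline prevalence and full persistence; at 50% persistence it is 7.3% to 14.0%. A reader might infer that the safety results will be inflated by these amounts, but the documents give no prevalence that would support this. The conclusion also depends on there being no general rule in the parts of 7.7 not supplied. This is a cheap reporting improvement, not a flaw that invalidates the safety analysis.

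**What to change.** First confirm whether 7.7 or the table shells already contain a treatment-emergent rule for PCSA. If not, add to 7.7.2, 7.7.3 and 7.7.5:

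- For each limit-based row, including the limit arm of QRS and PR but not the blood-pressure and QTcF-increase rows, keep the planned all-values count. Beside it report (a) the number meeting the limit at the pre-XEN496 baseline and (b) the number newly meeting it, with denominator the children who did not meet it at that baseline and have a later value.
- Baseline by group: OLE baseline for Placebo to XEN496, and the double blind baseline of SAP 6.1 for XEN496 Only, so that abnormalities arising in XPF-009-301 are not hidden.
- In the two banded ALT/AST rows, count as new only a rise from below the band, so that a fall into it is not called new.
- For age-banded limits (ECG and hemoglobin), state the age used and flag separately children whose status changes only because they moved to another band.

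Cost: a short SAP paragraph, two columns per PCSA table, and the primary study's baseline laboratory, ECG and pulse data for one group. The tables become slightly larger, and that group's baseline for these columns differs from the default in 7.1, which a footnote should say. No planned output is lost.

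### The white blood cell PCSA criterion in SAP 7.7.2 cannot work as written: *and* makes it empty, and its two limits do not fit any single unit

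*SAP*

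**What the plan says.** SAP 7.7.2 (Clinical laboratory evaluations) contains a PCSA table, numbered Table 4, with chemistry and hematology criteria. The white cell row is "White blood cells (WBC) <2.0 and >20,000", followed by the single unit 10^3 cells/uL. The same table has a platelet row, "Platelets (PLT) <50 x 10^3 cells/uL", and a composite hematology row, "Any Hematology Test".

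The criteria are used in two places in that section. For the listing, the SAP says that "potentially clinically significant abnormalities will be flagged in the listing". For the summary, it says: "The incidence of potentially clinically significant abnormalities (PCSA) for liver function (Table 4) for each scheduled visit will be summarized". The second sentence names liver function only, although the table also holds hematology rows.

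No other visible part of the SAP or protocol restates or corrects the white cell limits.

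**The concern.** The row has two faults, and curing one leaves the other.

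The first is the connector. A literal reading of *and* is reasonable because the same table uses it as a true conjunction, for example "ALT >=3xULN and Total Bilirubin >=2xULN", and also to bound ALT or AST between two multiples of the upper limit of normal. Where the SAP means alternatives, it writes *or* (QRS and PR intervals in 7.7.5) or gives the high and low limits separate lines (pulse rate in 7.7.3, heart rate in 7.7.5).

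The second is the unit. The two numbers share one printed unit but are on scales that do not match.

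The study's primary objective is long-term safety, and its endpoint in SAP section 2 includes clinically significant laboratory changes. This table is the visible rule that labels a laboratory value as potentially clinically significant. A programmer must either implement a rule that loses at least one side or guess what was meant.

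**Working it through.** **Inputs**, all from the PCSA table in SAP 7.7.2:

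- lower limit 2.0
- upper limit 20,000
- connector *and*
- printed unit 10^3 cells/uL
- for comparison, a platelet limit of 50 in 10^3 cells/uL

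**Step 1: the rule as written.** The set {x : x < 2.0 and x > 20,000} is empty, whatever unit x is in. A grid of values from 0 to 50,000 gives a count of 0.

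**Step 2: *or*, in the printed unit.**

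- Lower limit: 2.0 × 10^3 = 2,000 cells/uL.
- Upper limit: 20,000 × 10^3 = 20,000,000 cells/uL.
- The upper limit is 20,000,000 / 20,000 = 1,000 times a limit of 20,000 cells/uL. It is also 20,000 / 50 = 400 times the table's own platelet limit.

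**Step 3: *or*, in plain cells/uL.**

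- Lower limit: 2 cells/uL, which is 2 / 2,000 = 1/1,000 of the value in step 2.
- Upper limit: 20,000 cells/uL.

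**Step 4: the ratio of the limits.** In any single unit the ratio is 20,000 / 2.0 = 10,000, so a change of unit alone cannot help. If 2.0 is in 10^3 cells/uL and 20,000 is in cells/uL, the ratio is 20,000 / 2,000 = 10.

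**Step 5: which values are flagged.** The test values, in 10^3 cells/uL, were 0.5, 1.0, 1.9, 2, 5, 10, 19, 20, 20.1, 25, 50, 100 and 200.

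| Reading | Values flagged |
|---|---|
| *and*, as written | none |
| *or*, both limits in 10^3 cells/uL | 0.5, 1.0, 1.9 (low side only) |
| *or*, both limits in cells/uL | 20.1, 25, 50, 100, 200 (high side only) |
| *or*, 2.0 in 10^3 cells/uL and 20,000 in cells/uL | 0.5, 1.0, 1.9, 20.1, 25, 50, 100, 200 (both sides) |

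The last line is an illustration only; the documents do not confirm that reading.

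**Step 6: a decimal comma.** Reading 20,000 as 20.000 would reconcile the row with its unit. But the same row writes 2.0 with a decimal point, so this would need two number formats in one criterion.

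**The case against.** The best defence is that nobody would program an empty condition. On this view *and* loosely lists two one-sided flags. In the printed unit the lower limit then works, and it matches the platelet row. Plain cells/uL is not what the row prints, so the practical fault narrows to one number, the upper limit, whose scale does not fit its unit. This is probably how the error arose. But it concedes that the high flag fails in the printed unit and that the connector departs from the table's own usage.

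Second, the documents give no reference range for white cells, so calling a limit unusable is a judgement of scale. That is correct. Only the empty set and the 10,000-fold ratio follow strictly from the text.

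Third, a unit after 2.0 may have been lost in the public text of the table; the row also lacks the multiplication sign that the platelet row has. If each limit had its own unit in the source, only the connector would remain at fault. This cannot be excluded, but nothing visible supports it, and both figures appear intact. The separate tables, figures and listings templates might state the limits, but that would not correct the SAP.

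Fourth, the impact is small, and this stands in full. Observed values and changes from baseline are summarized. The SAP also plans this summary for hematology: "Shift from baseline to post-baseline laboratory findings at each visit in normal range criteria (Low, Normal, High"). For the listing, it states: "The listing will include normal ranges and clinical laboratory values that are outside the normal ranges". With about 40 subjects, the listing can be read directly.

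**Conclusion.** The concern holds, as a minor point. As written the criterion flags no value. With *or*, each single-unit reading loses one side: the upper limit sits at 20,000,000 cells/uL in the printed unit, or the lower limit sits at 2 cells/uL in plain cells/uL.

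The effect is confined to the white cell PCSA flag in the listing and to any white cell or composite hematology count that inherits it. Whether such a count will be produced is itself unclear, because the incidence sentence is worded for liver function. Efficacy analyses and error rates are not affected.

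The conclusion assumes that the row is printed in the source as it appears in the public SAP. It also rests on the judgement that white cell counts near 20 million or near 2 cells/uL will not be seen in practice.

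**What to change.** In the white cell row of the PCSA table in SAP 7.7.2, replace *and* with *or*, and state both limits in one unit, preferably the 10^3 cells/uL already used for platelets. The sponsor should confirm the intended upper limit, for example whether 20,000 was meant in cells/uL, which would be 20 × 10^3 cells/uL. The documents do not settle this, and it should not be left to the programmer.

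The cost is one line of text, best changed before the flags are programmed. If the final SAP is not reopened, the clarification should be recorded in the programming specification and described in the clinical study report, since SAP section 1 requires deviations from the plan to be described and justified there. No new data are needed and no other analysis changes.

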7.7.3 Vital signs

Observed and changes from OLE baseline for vital sign measurements will be summarized at each scheduled visit using descriptive statistics. In addition, summaries will be provided for the potentially clinically importance categories as presented below.

Table 5: Potentially Clinically Significant Vital Signs Abnormality Criteria

Parameter	Criterion			
	> ULN and increase of > 30			
Systolic Blood Pressure (mmHg)	< Lower limit of normal (LLN) and			
	decrease of > 20			
Directalia Direct Directory (mmIIa)	> ULN and increase of > 20			
Diastolic Blood Pressure (mmHg)	< LLN and decrease of $>$ 15			
Pulse Data (ham)	>= ULN			
Pulse Rate (bpm)	<= LLN			

Listings will be provided for vital sign data, and potentially clinically significant abnormalities will be flagged in the listing.

[figure not shown]
7.7.4 Physical examinations

All physical examination data will be listed using safety set.

7.7.5 Electrocardiograms

Observed and changes from OLE baseline of continuous ECG measurements will be summarized by treatment group and age groups (1 to 12 months and >12 to 84 months) at each scheduled visit. Additional summaries will be provided for ECG interpretation and will be summarized using frequency tables. Shift from baseline to post-baseline will also be provided for the ECG interpretation.

Potentially clinically significant abnormality categories listed below will be summarized using count and percentage.

Variable Name	Age group	Criterion
	NA	<= 300
QT interval corrected for heart rate by		>= 60 msec increase from
Fridericia's formula (QTcF) (msec)		baseline
		>= 500
OT Interval (msec)	NA	<= 300
QT Interval (msec)		>= 600
	1 to 12 months	>= 86 or $>=25%$ increase
OBS Interval (maga)		from baseline
QRS Interval (msec)	>12 to 84	>= 95 or $>= 25%$ increase
	months	from baseline
DP Internal (maga)	1 to 12 months	>= 141 or >= 25%
PR Interval (msec)		increase from baseline
	>12 to 84	>= 155 or $>= 25%$ increase
	months	from baseline
Haart rate (hpm)	1 to 12 months	>= 194
Heart rate (bpm)		<= 106
Haart rate (hpm)	>12 to 84	>= 123
Heart rate (bpm)	months	<= 62

Table 6: Potentially Clinically Significant ECG Abnormality Criteria

Listings will be provided for ECG data and potentially clinically significant abnormalities will be flagged in the listing.

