3.3 Study treatments and assessments

[figure not shown]
Total treatment duration per subject is estimated to be 36 months.

The treatment period begins with a dose transition/titration period. Subjects who received XEN496 in the preceding study will continue to receive XEN496 at the same dose, in a blinded manner, without any further titration.

Statistical Analysis Plan Protocol Number: XPF-009-302

Version: Final 1.0 Date: 04MAY2023 Page 13 of 47

The optimally-tolerated dose level established during the transition/titration period will be maintained throughout the duration of the open-label period unless dose adjustment is required.

A detailed description of procedures and assessments to be conducted during this study is summarized in the Scheduled of Study Assessments in Table 2 and Table 3 below.

DCON

Statistical Analysis Plan (SAP)

R XENON

Table 2: Schedule of Activities, Baseline and Treatment Period Up to 1 Year

Protocol Number: XPF-009-302

Version: Final 1.0 Date: 04MAY2023 Page 16 of 47

Protocol Number: XPF-009-302

[figure not shown]

Statistical Analysis Plan (SAP)

R XENON

C

R XENON

[figure not shown]

Protocol Number: XPF-009-302 Statistical Analysis Plan

Page 17 of 47

Page 18 of 47 Version: Final 1.0 Date: 04MAY2023

Protocol Number: XPF-009-302 Statistical Analysis Plan

[figure not shown]
Statistical Analysis Plan (SAP)

R XENON

C

Statistical Analysis Plan (SAP)

Table 3: Schedule of Activities, Long-term Treatment Period (up to 3 Years), and Taper and Follow-up Visits

Protocol Number: XPF-009-302

DocUUID : 33115ccb-9ab0-4f4a-bf62-222e09e4c4d6

Version: Final 1.0 Date: 04MAY2023 Page 20 of 47

Statistical Analysis Plan Protocol Number: XPF-009-302

K XENON

Statistical Analysis Plan (SAP)

CCI

R XENON

Cl	

Statistical Analysis Plan Protocol Number: XPF-009-302

Version: Final 1.0 Date: 04MAY2023 Page 21 of 47

Version: Final 1.0 Date: 04MAY2023 Page 22 of 47

Statistical Analysis Plan Protocol Number: XPF-009-302

[figure not shown]
Statistical Analysis Plan (SAP)

H XENON

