4 SAMPLE SIZE DETERMINATION

No formal sample size calculation has been performed. Only those subjects who have completed the previous study, XPF-009-301, are eligible to be enrolled into this study. Therefore, the expected total sample size will be up to approximately 40 subjects.

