6 STATISTICAL CONSIDERATIONS AND ANALYSIS

6.1 Derived Variables

The Table 4 provide the list of derived variables for demographic and baseline characteristics, various duration derivations, drug compliance, baseline derivations and other important derivations applicable for this study. Derived efficacy variables will be provided in Section 6.1.1

Table 4 Derived variables

Variables	Formula			
Demographic and Basel	Demographic and Baseline characteristics			
Age (in months)	integer ((Date of informed consent – Date of birth + 1)/ 30.4375)			
Age (in years)	integer ((Date of informed consent – Date of birth + 1)/ 365.25)			
OLE Baseline	Last non-missing value prior to start of study drug in OLE period i.e, Data collected at visit 22 or early termination (ET) visit in the primary study (XPF-009-301) will be considered. If any unscheduled non-missing value available after visit 22 or ET and before first dose in OLE, unscheduled visit value will be considered as baseline.			
Double blind Baseline	Last non-missing value prior to start of study drug in XPF-009- 301 study			
Derivation of Duration				
Study day at any visit	Date of interest – date of first dose of study drug in OLE +1, if date of measurement is on or after the first OLE dose date, or Date of measurement – first dose date, if date of measurement is prior to the first dose date. No Study Day 0 is defined			
Extent of Exposure (Days)	Date of last study medication intake in OLE – Date of first study medication intake in OLE + 1			
Extent of Exposure (Weeks)	Extent of exposure (days)/7			

[figure not shown]
For the computation of Bayley scores, age will need to be expressed in years, months, and days. The following algorithm can be used to derive these values:

TOTDAYS = ADT – BIRTHDT; AGEYRS = FLOOR (TOTDAYS / 365.25); /* age in years */

[figure not shown]

REMAINDR = TOTDAYS – (365.25*AGEYRS); AGEMTHS = FLOOR(REMAINDR / 30.4375); /* age in months */ AGEDAYS = ROUND(REMAINDR – (30.4375*AGEMTHS)); /* in days */

Visit windows for vitals, ECG, and labs are specified in the Table 5. If there is more than one observation within a visit window, the value closest to the nominal study day will be used. If two values are equidistant from the nominal study day, the later value will be used.

Version: Final 1.0 Date: 04MAY2023 Page 26 of 47

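### The heart-rate limits in SAP Table 6 change so sharply at 12 months that both age bands cannot suit children near that age, so the abnormality counts will partly reflect age

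*SAP*

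**What the plan says.** SAP section 7.7.5 summarises ECG measurements in two "age groups (1 to 12 months and >12 to 84 months"). Table 6 then gives the limits for potentially clinically significant values, and "Potentially clinically significant abnormality categories listed below will be summarized using count and percentage". The same limits drive the flags in the ECG listing.

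For heart rate, Table 6 has:

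| Age band | Flagged high | Flagged low |
|---|---|---|
| 1 to 12 months | 194 bpm or more | 106 bpm or less |
| Over 12 to 84 months | 123 bpm or more | 62 bpm or less |

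There is no band in between, and the older limits are constant over 72 months of age. QRS and PR also have a criterion for change from baseline; heart rate has none, so the fixed limits alone decide its flag. The SAP gives no source for them.

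It also does not say which age selects the band. The general age variable in section 6.1 is age at consent: "integer ((Date of informed consent – Date of birth + 1)/ 30.4375"). Treatment is long: "Total treatment duration per subject is estimated to be 36 months". On numbers, section 4 says that "the expected total sample size will be up to approximately 40 subjects". The text available gives no age distribution.

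**The concern.** The documents place no clinical event at 12 months that would make heart rate drop by tens of beats, yet the high limit falls by 71 bpm and the low limit by 44 bpm at that age. A rate in the middle of the infant range is abnormal under the older limits, and a rate in the middle of the older range is abnormal under the infant limits. If normal rates change gradually, at least one set of limits misclassifies children close to the boundary.

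Clinically significant ECG changes are part of the primary safety endpoint (SAP section 2). The study has no concurrent control. If flags depend on which side of 12 months a child falls, the heart-rate counts partly describe the age of the sample rather than the drug. With at most about 40 subjects, a few such flags visibly move a percentage.

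**Working it through.** The plan states no figure on this point to reproduce. The four heart-rate limits come from SAP Table 6. Everything about the distribution of heart rate is an assumption and is marked as such.

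**1. Overlap of the unflagged ranges (whole bpm, no assumption)**
- Younger band: 107 to 193, which is 87 values; midpoint (107 + 193)/2 = 150.
- Older band: 63 to 122, which is 60 values; midpoint (63 + 122)/2 = 92.5.
- Shared: 107 to 122, which is 16 values.
- Unflagged under the infant limits but high under the older ones: 123 to 193, 71 of 87 (82%), including 150.
- Unflagged under the older limits but low under the infant ones: 63 to 106, 44 of 60 (73%), including 92.5.
- Step at 12 months: high limit 194 to 123, −71/194 = −37%; low limit 106 to 62, −44/106 = −42%.

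**2. Smallest possible misfit at 12 months (assumes gradual change and normality)**

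If heart rate changes gradually, children just below and just above 12 months have nearly the same distribution. A rate of 106 or less is low under the infant limits, and 123 or more is high under the older limits, so only rates between 106 and 123 escape both. For a normal distribution with standard deviation s, the share escaping both is largest when the mean is at the centre, 114.5. The half-width is 8.5, so:

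minimum share flagged by one band or the other = 2 × [1 − Φ(8.5/s)]

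The SD is not in the documents. If each pair of limits is a central 95% or 98% range, s is the half-width (44 or 30.5 bpm) divided by 1.960 or 2.326:

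| Limits read as | s from infant band | s from older band |
|---|---|---|
| central 95% | 22.4 | 15.6 |
| central 98% | 18.9 | 13.1 |

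- Smallest s, 13.1: 2 × [1 − Φ(0.648)] = 52%.
- Largest s, 22.4: 2 × [1 − Φ(0.379)] = 70%.

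Any other mean gives a larger total. This is the sum of the two bands' shares, not the rate in either one. At least one band must therefore flag half of it or more, that is 26% to 35% of unaffected children of this age.

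**3. Which side carries the misfit (depends on where true rates lie)**

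Share of unaffected children just over 12 months flagged high, P(rate ≥ 123), with the limits read as 2/98, 2.5/97.5 or 5/95 percentiles:

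| Rates just after 12 months | Mean (bpm) | 2/98 | 2.5/97.5 | 5/95 |
|---|---|---|---|---|
| still follow the infant band | 150 | 90% | 89% | 84% |
| halfway between the bands | 121.25 | 46% | 46% | 47% |
| already follow the older band | 92.5 | 2% | 2.5% | 5% |

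Reading the limits as a central 98% range widens the extremes slightly, to 92% and 1%. In the last row the high flags are at their nominal rate, but the misfit moves to infants just under 12 months, who would be falsely flagged low.

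**The case against.** The strongest objection is that the documents give no heart rates by age, so the direction and size of any error are unknown. That stands. A reader might infer that toddlers are over-flagged as high and that low rates in toddlers are missed. This follows only if rates just after 12 months are still well above the older band's centre. It is also tempting to put a percentage on each age by drawing a line between the two bands, but the answer depends on where the older limits are assumed to fit. With a line from 6.5 months and central 95% limits, 71% of unaffected 18-month-olds are flagged high if the older limits fit at 48 months, and about 27% if they fit at 24 months. Nothing in the documents chooses between these.

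A reader might also infer that a child changes category on passing 12 months and then appears as a new abnormality on drug. That needs the band to follow age at the ECG. If age at consent selects it, no child switches; instead, a child aged 12 months at consent is judged by infant limits to about 48 months of age (12 + 36). The misfit remains, because children on either side of 12 months at consent are still judged by very different limits.

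It is fair to add that no hypothesis test uses these flags. Observed values, changes from OLE baseline, ECG interpretation and listings are also reported, and section 7.7.3 flags pulse rate separately against normal limits. These reduce the consequence but do not correct the Table 6 counts. The smaller steps in QRS (86 to 95) and PR (141 to 155), about 10% each, prove nothing, since heart rate need not step by the same proportion.

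**Conclusion.** The point holds without a direction. That the two heart-rate ranges share only 16 whole-bpm values is plain from Table 6. Given gradual change with age, the limits cannot suit children on both sides of 12 months. Given also normality and an SD of 13 to 22 bpm, at least about 52% to 70% of unaffected 12-month-olds would be flagged by one band or the other. The share flagged high just over 12 months could be anywhere from 2-5% to 84-90%.

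The heart-rate counts and listing flags would therefore partly reflect age rather than drug. How many subjects this touches cannot be computed, because the age mix is not given, so the documents do not support saying that age would dominate the counts. This is worth correcting before the tables are produced, as a weakness in a descriptive display that supports the primary safety endpoint.

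**What to change.** In Table 6, replace the two heart-rate bands with narrower age bands, or with age-specific percentile limits, taken from one cited paediatric reference so that the limits change gradually across 12 months. State that age at the ECG selects the band. No replacement limits are proposed here; they should come from the reference that the sponsor cites.

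The cost is a table edit and a lookup in the ECG program, with no new data. Counts will differ from the current two-band display, which can be kept as a secondary table.
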